4.2. Exclusion Criteria

Any potential subject who meets any of the following criteria will be excluded from participating in the study:

1. Subjects who are not expected to survive for more than 48 hours.
2. Subjects who have had major thoracic or abdominal surgery in the 6 weeks prior to randomization.

3. Subjects who received (within 12 months prior to screening) or who are currently on a waiting list for a bone marrow, stem cell, or solid organ transplant, who received radiation or chemotherapy (within 12 months prior to screening), or who are currently taking immunosuppressive medication (refer to Section 8, Pre-study and Concomitant Therapy).
4. Subjects who have a known or suspected immunodeficiency (except immunoglobulin A [IgA] deficiency), such as a known human immunodeficiency virus infection.
5. Subjects who have a history of or concurrent illness (beyond a defined comorbid condition for severe RSV disease) that in the opinion of the investigator, might confound the results of the study or pose an additional risk in administering study drug to the subject, or that could prevent, limit, or confound the protocol-specified assessments such as liver or renal insufficiency; significant cardiac, vascular, pulmonary, gastrointestinal, endocrine, neurologic, hematologic, rheumatologic, metabolic disturbances, or genetic diseases that result in immunosuppression. These may include, but are not limited to bacteremia, organ dysfunction, or other severe comorbidities.
6. Subjects who have a poorly functioning gastrointestinal tract (ie, unable to absorb drugs or nutrition via enteral route).

NOTE: The use of IV fluids is not exclusionary so long as the investigator believes the subject's gastrointestinal tract still functions properly (ie, is able to absorb drugs or nutrition).
7. Subjects being treated with extracorporeal membrane oxygenation.
8. Subject receiving chronic oxygen therapy at home prior to admission.
9. Subjects who have taken any disallowed therapies as noted in Section 8, Prestudy and Concomitant Therapy, before the planned first dose of study drug.

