The time to clinical stability is defined as the time from initiation of study treatment until the time at which the following criteria are met: return to pre-RSV infection status (hereafter referred to as “normalization”) of blood oxygen level (ie, no additional requirement of supplemental oxygen compared with pre-RSV infection status), normalization of oral feeding, normalization of respiratory rate, and normalization of heart rate. Normalization criteria will be specified in the SAP. Subjects for which no timepoint could be established (eg, withdrawal of informed consent before reaching the endpoint or no clinical stability at last observation) will be (right-)censored at the latest timepoint at which it could be established that clinical stability was not reached. The differences in time to clinical stability of active dose regimens versus placebo treatment will be estimated using a Cox proportional hazard model; as baseline covariates, stratification factors,

absence/presence of other viral or bacterial infections, and baseline \log_{10} viral load will be added. Treatment effect versus placebo will be reported, including 95% confidence intervals. In case the proportional hazards assumption is not satisfied, appropriate sensitivity analyses will be performed as detailed in the SAP.

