 - Respiratory distress (eg, cyanosis, tachypnea, retractions)
 - Low oxygen saturation
 - Tachycardia
 - None of these
 - 1.2 Was the subject hospitalized due to any of these clinical signs? (note all that apply)
 - Dehydration/difficulty feeding
 - Listless or unresponsive
 - Fever
 - Need for clinical monitoring
 - None of these
 - 1.3 Was the subject hospitalized for any other reason?
 - No
 - Yes → *(specify pop-up: please specify [256 character free-text])*

[Intro screen for current/recent status assessment]

Please record the following information regarding the subject's status during the past 12 hours.

1. Describe the subject's reported worst activity level during the past 12 hours (select one)
 - Alert and active/normal sleep
 - Irritable/restless/agitated
 - Floppy/lethargic/poor interaction
 - Only responds to pain/unresponsive

2. Describe how the subject slept during the past 12 hours (select one)
 - Normal
 - Occasional restlessness/disturbed
 - Restless/disturbed much of the time
 - Comatose

3. Signs of increased work of breathing during the past 12 hours
 - 3.1. Did the subject show any of these signs (or reports) of increased work of breathing during the past 12 hours? (note all that apply)
 - Subcostal retractions
 - Intercostal retractions
 - Tracheosternal retractions
 - Tachypnea [*tachypnea needs defined within the system WHO values pop-up?*]
 - None of the above [*cannot be checked if any other options selected*]

 - 3.2. Did the subject show any of these signs (or reports) of increased work of breathing during the past 12 hours? (note all that apply)
 - Nasal flaring
 - Head bobbing
 - Grunting
 - Other signs of increased work of breathing not already reported
 - None of the above [*cannot be checked if any other options selected*]

4. During the past 12 hours, are there observations/reports of the subject experiencing any of the following? (note all that apply)
 - Cyanosis
 - Apnoea
 - Cough
 - Nasal secretions
 - Wheezing
 - None of the above reported [*cannot be checked if any other options selected*]

5. How did the subject feed in the past 12 hours? (select one)

- >75% of normal amount of feeds via usual route
- 50% to 75% of normal amounts of feeds via usual route
- <50 % of normal feeds or needing NG feeds or IV fluids

Please record the following information regarding the subject's status now.

6. Describe the subject's activity level now (select one)

- Alert and active/normal sleep
- Irritable/restless/agitated

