Requirement for supplemental feeding/hydration	
Does the subject require supplemental feeding/hydration (e.g. IV catheter/nasogastric tube) after first dose of study drug?
 
Categories will be Yes (1) or No (0).
 
Only derive this parameter for subjects that didn't require supplemental feeding/hydration before first dose of study drug.

Time to end of intensive care	The time from first study drug intake until the time of

Measurement	Formula
unit (ICU) stay (hours) [Time-to event]	
discharge from the ICU after which the subject was not readmitted to the ICU (= event)
 
Subjects who complete or withdraw from the study prior to the event will be censored at the date of completion or withdrawal. If the time is not available they will be censored at 12:00. In case of death the subject will be censored at the maximum observed number of hours until the occurrence of the event or censoring for all subjects achieving the event or being censored because of study completion or withdrawal. If no admittance to the ICU was necessary, the value will be set to 0.
 
(Date and time of event or censoring - date and time of first dose of study drug)/3600, rounded to one decimal

Time to end of Oxygen supplementation (hours) [Time-to event]	
The time from first dose of study drug start of oxygen supplementation to the last end date and time of any oxygen supplementation (= event) in hours (Oxygen supplementation is indicated on the Oxygen Supplementation form: Type of supplemental oxygen administration.). (Note: it is not necessary that the subject started on oxygen at baseline.)
 
If the end date is missing, the end date is considered to be after study completion or withdrawal.
 
Subjects who complete or withdraw from the study prior to the event will be censored at the date of completion or withdrawal. If the time is not available they will be censored at 12:00. In case of death the subject will be censored at the maximum observed number of hours until the occurrence of the event or censoring for all subjects achieving the event or being censored because of study completion or withdrawal.
 
If no oxygen supplementation was necessary after first dose of study drug, the value will be set to 0 hours.
 
(Date and time of event or censoring - date and time of first dose of study drug)/3600, rounded to one decimal

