Time to end of noninvasive mechanical ventilation support (hours) [Time-to event]	
The time from first dose of study drug to the last end date and time of noninvasive mechanical ventilation and invasive mechanical ventilation support (= event) in hours. Noninvasive mechanical ventilation and invasive mechanical

Measurement	Formula
	
ventilation are defined as indicated on the Oxygen Supplementation form: Type of supplemental oxygen administration.
 
Derivation similar as “Time to end of Oxygen supplementation”

Time to end of invasive mechanical ventilation support (hours) [Time-to event]
	
The time from first dose of study drug to the last end date and time of invasive mechanical ventilation support (= event) in hours. Invasive mechanical ventilation support is defined as indicated on the Oxygen Supplementation form: Type of supplemental oxygen administration.
 
Derivation similar as “Time to end of Oxygen supplementation”

Time to end of supplemental feeding/hydration (hours) [Time-to event]
	
The time from first dose of study drug to the last end date and time of supplemental feeding/hydration (e.g. IV catheter/nasogastric tube) (= event) in hours.
 
Derivation similar as “Time to end of Oxygen supplementation”

Time to return to pre-RSV disease level for respiratory rate (hours) [Time-to event]
	
The time from first dose of study drug until the time to return to pre-RSV disease level. The return to pre-RSV disease level occurs when the observed value of the parameter is indicated by the investigator as normal, and no later observed values are indicated by the investigator as abnormal (=event).
 
Normalization of respiratory rate (RR) will be derived from the answer to the corresponding question in the questionnaire “is this Respiratory Rate value normal for this patient?”
 
If no deterioration from pre-RSV disease levels occurred, the time will be set to time of first dose of study drug and the value will be set to 0 hours.
 
Subjects with an abnormal value at the last assessment will be censored at that time. Subjects for which this last assessment is the baseline assessment will be censored at time 0.

Measurement	Formula
	(Date and time of event or censoring - date and time of first dose of study drug)/3600, rounded to one decimal

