Time to return to pre-RSV disease level for heart rate (hours) [Time-to event]	
Idem as Time to return to pre-RSV disease level for respiratory rate (hours) but for heart rate.
 
Normalization of heart rate (HR) will be derived from the answer to the corresponding question in the questionnaire “is this Pulse value normal for this patient?”

Time to clinical stability (hours) [Time-to event]	
The time from first dose of study drug until the time at which the each of the following criteria are met (=event):
 
 • Normalization of Oxygen supplementation (as in parameter Time to end of Oxygen supplementation), • Normalization of feeding/hydration (as in parameter Time to end of supplemental feeding/hydration) , • Normalization of respiratory rate (as in parameter Time to return to pre-RSV disease level for respiratory rate), and • Normalization of heart rate (as in parameter Time to return to pre-RSV disease level for heart rate). 
In case any of the four components is censored, the time to clinical stability will also be censored at the first time-point of the censored component.
 
Subjects who complete or withdraw from the study prior to the event will be censored at the date of completion or withdrawal. If the time is not available they will be censored at 12:00. In case of death the subject will be censored at the maximum observed number of hours until the occurrence of the event or censoring for all subjects achieving the event or being censored because of study completion or withdrawal.
 
(maximum(Date and time of event criteria or censoring) - date and time of first dose of study drug)/3600, rounded to one decimal

Time to return to pre-RSV disease level for body temperature (hours), [Time-to event]	
The time from first dose of study drug until the time to return to pre-RSV disease level. The return to pre-RSV disease level occurs when the observed value of the parameter is within the normal range (=event).
 
If no deterioration from pre-RSV disease levels occurred, the

Measurement	Formula										

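### The feeding component of time to clinical stability in the SAP records when tube or IV support ends, not the return to pre-RSV oral feeding that the protocol requires

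*SAP*

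**What the plan says.** Protocol 11.3 defines time to clinical stability as the time from treatment initiation until four features have returned to their pre-RSV state: oxygen level, and then "normalization of oral feeding, normalization of respiratory rate, and normalization of heart rate". It leaves the detail open: "Normalization criteria will be specified in the SAP".

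SAP 5.3.1.3 fills in the feeding criterion as "Normalization of feeding/hydration (as in parameter Time to end of supplemental feeding/hydration". The event for that parameter is the last end date "and time of supplemental feeding/hydration (e.g. IV catheter/nasogastric tube) (= event) in hours". Neither the amount eaten nor the child's feeding before RSV enters the definition.

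The remaining rules are borrowed from the parameter for end of oxygen supplementation in the same section:
- A missing end date is treated as falling after study completion or withdrawal, so the child is censored.
- Where no support was given: "If no oxygen supplementation was necessary after first dose of study drug, the value will be set to 0 hours". Applied to feeding, no tube or IV after first dose means 0 hours.
- In the composite, one censored component censors the whole endpoint. Otherwise the composite time is the latest of the four component times.

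**The concern.** The protocol lets the SAP specify the criteria. It does not let the SAP drop the two things that define this component, namely oral intake and comparison with the pre-RSV state. Stopping a drip or nasogastric tube is a different event from eating normally again.

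Feeding is also the only component left without a pre-RSV anchor. Respiratory rate and heart rate are judged by whether the value is normal for that patient. Oxygen is protected by exclusion criterion 8 in Protocol 4.2: "Subject receiving chronic oxygen therapy at home prior to admission". No matching exclusion covers long-term tube feeding. Criterion 6 concerns only a gut that cannot absorb enterally. Neuromuscular impairment, Down syndrome, congenital disease and prematurity are eligible under Protocol 3.1.1, and Protocol 7 allows study drug by nasogastric tube.

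Time to clinical stability is a named secondary endpoint. SAP 5.3.2.3 analyses it by Kaplan-Meier, Cox, logrank and Gehan-Wilcoxon methods and relates it to viral load. A report under the protocol's label would describe feeding recovery that the derivation did not measure.

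**Working it through.** No sample size, power or alpha figure depends on this definition, so there is no stated figure to reproduce. The check applies the SAP rules to three hypothetical children.

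**Rules (SAP 5.3.1.3)**
- Feeding time = 0 h if no tube or IV after first dose; censored at study end if support has no end date; otherwise the last end time of support.
- Stability time = max(oxygen, feeding, respiratory rate, heart rate); censored if any component is censored.

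**Assumed inputs, for illustration only:** oxygen 60 h, respiratory rate 60 h, heart rate 48 h; study end 27 × 24 = 648 h.

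| Child | Feeding component | Stability under the SAP |
|---|---|---|
| 1. Nasogastric feeding for the acute illness, stopped at 48 h | event at 48 h | max(60, 48, 60, 48) = 60 h, event |
| 2. Nasogastric feeding since before RSV, recorded as supplemental, still ongoing | censored at 648 h | censored at 648 h |
| 3. Takes 50-75% of normal feeds until 96 h, no tube or IV | event at 0 h | max(60, 0, 60, 48) = 60 h, event |

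Child 1 is handled as the SAP intends. Child 2 is back to the pre-RSV state at 60 h but is never counted as an event. Child 3 is declared stable 96 − 60 = 36 h before intake recovers; under the protocol's definition the time would be max(60, 96, 60, 48) = 96 h. Had child 3's intake recovered at or before 60 h, the composite would be correct. The error on the composite therefore appears only when feeding recovers last.

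**How many children**
- Child 2 type: the documents give no frequency. If all such children are in the comorbid group, the 20% cap in Protocol 3.1.1 gives an upper bound of 0.20 × 120 = 24 or 0.20 × 180 = 36, apart from the allowance for extra comorbid children aged 24-36 months. The range is 0 to about 24 of 120, or 0 to about 36 of 180.
- Child 3 type: no frequency is given either, and such children need not be comorbid. The protocol foresees them: the screening question in Attachment 5 lists difficulty feeding among the reasons for admission, and clinician PRESORS item 5 has a 50-75% category that involves no tube.

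**The case against.** **The SAP is authorised to set the criteria, and support is a reasonable proxy.** Protocol 9.2 itself lists the need for IV or nasogastric hydration and feeding as a clinical-course measure, and the oxygen component is also support-based. This has force for using end of support as one element. It does not explain leaving out intake and the pre-RSV reference, and for a child who never had support the proxy carries no information.

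**Whether tube-fed children are lost depends on a form not in the documents.** A reader might infer that children tube-fed before RSV can never reach stability. That goes too far. If the case report form does not record usual tube feeds as supplemental, or the feeding ends before study end, the child is not censored for this reason. What stands is that the SAP does not limit the term to support above pre-RSV status. Nor is there a basis for a prevalence estimate within the 0-to-cap range: the 20% is a ceiling, comorbid enrolment opens only after IDMC review and recommendation, and the group includes any infant under 1 year born before 37 weeks.

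**Feeding is analysed elsewhere.** A reader might infer that a drug effect on feeding could not be seen in the trial. It could. SAP 5.3.2.3 analyses the need for supplemental feeding and the time to its end, and combines the p-values. Feeding items enter the PRESORS severity scores (SAP 5.4.1), and the items are tabulated at baseline and Days 7, 14 and 28 (SAP 5.4.2). The loss is confined to this component of the composite, for children without tube or IV support.

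**No bias between arms is shown.** Randomization is stratified by comorbidity and the Cox model includes the stratification factors. This stands: the documents support lost or mistimed events, not a directional error.

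**Conclusion.** The SAP definition does not measure what the protocol names, and no other section corrects it. Two consequences follow from the rules as written:

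1. Reduced oral intake without tube or IV scores 0 hours on the feeding component. The composite is then too early whenever feeding is the last component to recover. The 0 hours belongs to the component; it does not mean that the child counts as clinically stable at first dose, because the composite takes the maximum of four times.
2. Pre-RSV tube feeding that is recorded as supplemental and continues to study end censors a child who is back to the pre-RSV state.

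The size is uncertain: 0 to about 24 of 120 or 36 of 180 for the second, under the assumption that these children all fall within the capped comorbid group, and unquantified for the first. The zero-hour rule reaches feeding through the instruction to derive it like the oxygen parameter, not through a sentence of its own. The primary endpoint, alpha and sample size are untouched. The correction should be made before unblinding, but it does not threaten the trial's main conclusion.

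**What to change.** In SAP 5.3.1.3, define the feeding component as the later of two times:
- the end of supplemental feeding or hydration above pre-RSV status, with 0 hours if there was none; and
- the first clinician PRESORS item 5 rating (Protocol Attachment 5) of ">75% of normal amount of feeds via usual route" with no later lower rating.

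State explicitly that a tube in use before RSV is the usual route. This is needed because the lowest category of the same item also names the need for nasogastric feeds, so a long-term tube-fed child could otherwise be placed in either the best or the worst category. Caregiver feeding item 11 in the Attachment 5 diary (item 10 in the SAP scoring table) can refine timing after discharge. Keep time to end of supplemental feeding/hydration as a separate endpoint.

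Cost: SAP wording and one derivation, with no new data. Under Protocol 9.1.1, item 5 is completed twice daily in hospital and at the Day 7, 10, 14 and 28 visits, and the caregiver diary is completed at least daily to Day 28. There are three downsides. Clinician ratings after discharge exist only at visits. The >75% category only approximates pre-RSV intake. PRESORS is still being validated (SAP 5.4.1).

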5.3.2. Analysis Methods

Descriptive statistics

The descriptive statistics that will be shown will include the number of subjects, mean, standard deviation, standard error, 95% confidence interval, median, range and interquartile range.

Time-to event variables

All Time-to event variables will be analyzed using Kaplan-Meier estimates analysis, A summary table including number of subjects included in the analysis, number of subjects censored, 25th and 75th percentiles and median time-to event, with 95% confidence intervals based on log-log transformation method, will be presented. The data will be presented graphically using the Kaplan-Meier estimate of the survival function by treatment.

Accelerated failure time (AFT) model

When indicated time-to event variables will be compared between each active treatment group and placebo using an accelerated failure time (AFT) model. The distribution to be used will be determined based on the goodness of fit using Akaike’s information criterion and will be selected from the following parametric families: lognormal, log-logistic, or Weibull. The AFT model will include the fixed, categorical effects for treatment (with placebo as the reference) and stratification factor.

A summary of information from the final AFT model will include parameter estimates and associated standard errors, estimated accelerated failure time ratios versus placebo and associated 95% confidence intervals, and p-values. The survival curves per treatment group of the accelerated failure time model will also be shown.

Logistic regression model

A stratified logistic regression model will be used to analyze the binary outcome, with treatment group and stratification factors as fixed effect, will be used to obtain the odds ratios (95% CI) for each comparison versus placebo.

The odds ratios including 95% confidence interval of active groups versus placebo will be derived from the final model using appropriate contrasts. Exact logistic regression models will be used in case the incidence of the events is low (< 10 events).

Model building procedure

In the statistical models following predictive covariates and or baseline indicators may be included: baseline \log_{10} viral load, smoking in the environment (yes/no), presence/absence of comorbid diseases, presence/absence of comorbid diseases associated with risk for lower respiratory tract disease, presence/absence of other conditions/therapy of potential interest, days since symptom initiation, RSV subtype, use of corticosteroids, supplemental oxygen at baseline, absence/presence of other viral or bacterial infections and age as continuous variable.

Stepwise forward selection will be used to identify the prognostic factors in combination with backward elimination. A significance value of 0.05 is required for a variable to enter the model and a significance value of 0.10 is required to stay in the model.

